4.1 Rationale for study design

The COMBI-AD study demonstrated significant improvements with dabrafenib and trametinib in the adjuvant treatment of stage III BRAF V600E/K mutation-positive melanoma and this combination is already recommended in treatment guidelines as a new standard of care ([NCCN 2017](#)).

Considering that pyrexia is a common and well-characterized adverse event, it is observed early in the course of dabrafenib and trametinib treatment and presenting multiple occurrences in some patients. Therefore, an adapted pyrexia AE-management algorithm will be prospectively implemented in this single-arm, multicenter, phase IIIb study in order to evaluate the reduction of adverse outcomes of pyrexia (grade 3/4 pyrexia, hospitalization due to pyrexia, and permanent treatment discontinuation due to pyrexia).

This single-arm study does not have a control population. The COMBI-AD study will serve as a benchmark for the incidence of pyrexia over 12 months of treatment, an endpoint that is valid because most events were observed within this period. A phase IIIb, single-arm, non-randomized trial design for this study was chosen over a controlled study to compare AE management algorithms because of logistical issues, as it cannot be predicted which subjects will develop pyrexia while on study treatment. Also, unblinded randomization of different AE management algorithms in a controlled study would be subject to selection bias, and the COMBI-AD study provides a benchmark for historical comparison.

This study will consist of two periods for enrolled subjects: the Treatment period and the Follow-up period. The Treatment Period will enroll approximately 600 subjects with high-risk stage III BRAF V600E/K mutation-positive melanoma after complete resection. Subjects fulfilling the eligibility criteria will be enrolled to receive dabrafenib and trametinib for up to 12 months. The Follow-up Period will include all subjects from study treatment discontinuation through EoS, death, withdrawal of consent, or lost to follow-up, whichever occurs first.

The primary endpoint in the Treatment Period is the composite rate of grade 3/4 pyrexia, hospitalization due to pyrexia, or permanent treatment discontinuation due to pyrexia among all treated subjects for up to twelve months of therapy.

The rate of the composite primary endpoint is defined as the total number of subjects experiencing at least one of the three components of the composite endpoint (i.e., Grade 3/4 pyrexia, hospitalization due to pyrexia, or permanent treatment discontinuation due to pyrexia), divided by the total number of subjects treated in the study. In the COMBI-AD study, 23 (5%)

subjects had grade 3/4 pyrexia, 46 (11%) subjects were hospitalized due to pyrexia and 38 (9%) subjects permanently discontinued due to pyrexia. In total, in COMBI-AD, 87 out of 435 subjects in the treatment arm (20%) developed either grade 3/4 pyrexia or hospitalization due to pyrexia or discontinued due to pyrexia. This rate of 20% will be used as the historical control rate for the assessment of pyrexia management algorithm in this study.

In the absence of control arm in the study, the composite rate due to adverse outcomes of pyrexia in the study will be compared with the 20% historical rate observed in COMBI-AD study.

As this is the first trial to prospectively test the algorithm, an IA of the primary endpoint and secondary efficacy endpoint RFS at 6 months is planned which will allow assessing the futility of the adapted algorithm. Please refer to [Section 4.4](#).

The secondary endpoints of RFS and OS (12 and 24 months) will be assessed across both periods in the study based on efficacy assessment guidelines in the COMBI-AD study. Subjects will be followed up to EoS, death, withdrawal of consent, or lost to follow-up, whichever occurs first, but will only have on-study tumor assessments through 24 months after first dose of study treatment. Other secondary endpoints include the evaluation of the overall adverse events rate leading to permanent treatment discontinuation at 12 months, overall safety and tolerability, as well as patient-reported outcomes (FACT-M) through 24 months.

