	
 • Women of child-bearing potential, defined as all women physiologically capable of becoming pregnant, must use highly effective methods of contraception during dosing and for 16 weeks after stopping treatment with trametinib or 2 weeks after stopping treatment with dabrafenib whichever is longer. • Women who are nursing during dosing and for 16 weeks after stopping study treatment • Male subjects (including those that have had a vasectomy) taking study treatment must use a condom during intercourse, and for 16 weeks after stopping treatment, and should not father a child during these periods
Study treatment	The combination of dabrafenib 150 mg twice a day and trametinib 2 mg once a day
Efficacy assessments	Tumor assessment by investigator's assessment measured at Month 3, 6, 12, 15, 18 and 24
Key safety assessments	
 • Physical examination • ECOG PS • Weight and vital signs • Ophthalmic examination • 12-lead ECGs • ECHO/MUGA • Laboratory assessments, including hematology, chemistry, and coagulation • Monthly pregnancy testing for women of child-bearing potential. • Adverse events (AEs), the severity, the relationship to study treatment and the seriousness
Other assessments	
 • Patient reported outcome assessment by Melanoma Subscale of the FACT M

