Approximately 600 subjects will be enrolled to receive dabrafenib (150 mg BID) and trametinib (2 mg once daily) combination therapy for 12 months. At Day 1, subjects will be instructed on the pyrexia management algorithm (refer to [Section 6.5.1.1](#)). Doses of study treatment may be modified and/or interrupted for management of toxicities associated with study treatment ([Section 6.5.1.1](#)). There will be an IA of the primary endpoint and secondary efficacy endpoint RFS when approximately the first 200 subjects dosed have been followed for 6 months (either completed 6 months of treatment or discontinued treatment earlier (see [Section 4.4](#)).

For this study, one study month is equal to 4 weeks or 28 days.

This study consists of two Periods for Enrolled subjects:

- Treatment Period – subjects will receive up to 12 months of treatment (refer to the schedule as noted in [Table 8-1](#)).
- Follow-up Period – subjects will be followed from treatment discontinuation through 24 months from their first dose date for relapse; and will be followed for overall survival through withdrawal, lost to follow-up, death, or the end of study (see definition in [Section 9.2](#)), whichever occurs first. Follow-up will start once: 1) treatment is completed; or 2) is prematurely discontinued and continue until withdrawal, lost to follow-up, death, or the end of study even if disease recurs. Follow-up contact prior to disease recurrence and through the 24 month assessment will include clinic visits (refer to the schedule as noted in [Table 8-2](#)). Follow-up after disease recurrence and until EoS should follow the schedule as noted in [Table 8-3](#).

Figure 3-1 Study design

4 Rationale

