If early treatment discontinuation occurs due to reason other than disease relapse or a subject has completed treatment and has not relapsed, refer to [Table 8-2](#).

Table 8-2 Follow-up (Pre-Relapse) Assessment Schedule

	Pre-Relapse Visit & Assessment Schedule ¹							
Visit Name	Month 3	Month 6	Month 12	Month 15	Month 18	Month 24	Survival Contact (every 3 mo) ²	End of Study (EoS) ³
Physical Examination	X	X	X	X	X	X		X ³
ECOG Performance Status	X	X	X	X	X	X		X ³
Chest, abdomen and pelvic CT scans ⁴	X	X	X	X	X	X		X ³
Dermatologic Assessment	X	X	X	X	X	X		X ³
Patient reported outcomes	X	X	X	X	X	X		X ³
Any anti-neoplastic therapy (including surgery, radiotherapy, medications) since discontinuation of study treatment including Best Response	X	X	X	X	X	X	X	X
Survival Follow Up	X	X	X	X	X	X	X	X
Disposition Assessment (at the end of each study period)								X

¹ Follow-up will start once treatment is completed or discontinued and should continue through EoS Visit, withdrawal or death, even if disease recurs. Follow-up visits prior to disease recurrence should follow [Table 8-2](#), and should be clinic visits through the Month 24 Assessment. Follow-up visits after the Month 24 Assessment are not required to be clinic visits and the information collected will be limited to the following: any radiotherapy; surgical procedure or new anti-cancer therapy initiated until EoS visit, withdrawal or death; best response to any follow-up treatment; and survival data. For example, if a subject discontinues treatment at Month 2 for reason other than disease relapse, the EoS should be performed according to [Table 8-1](#) and the follow-up assessments would start at Month 3 according to [Table 8-2](#) until EoS, withdrawal or death. Follow-up after disease relapse should follow the schedule in [Table 8-3](#).

² Survival follow-up after the Month 24 assessment should be conducted every 3 months until withdrawal, death, or study end (whichever occurs first), and can be done via phone contact.

³The EoS visit should be completed at withdrawal, lost to follow-up, death, or at the end of study (see definition in [Section 9.2](#)), whichever occurs first. If the EoS visit occurs after the Month 24 visit, a clinic visit is not required and the information collected will be limited to the following: anti-cancer therapy, best response to any follow-up treatment, and survival data

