8.3.1.1 Assessment Guideline

Assessments must be performed on a calendar schedule and should not be affected by dose interruptions/delays. For post-baseline efficacy assessments Month 1 through Month 12, a window of ± 3 days (physical exam) or ± 7 days (CT scans, dermatologic skin assessment) is permitted to allow for flexible scheduling. After Month 12/EoT a post-baseline assessment window of ± 14 days is permitted.

The following are required for efficacy assessment:

- Clinical examination
- Diagnostic quality, contrast-enhanced CT scan of the chest, abdomen and pelvis should be performed at baseline and subsequent timepoints as indicated in [Table 8-1](#), [Table 8-2](#), and [Table 8-4](#). Intravenous contrast should be used for the CT scans preferably with oral contrast as well. CT contrast of the chest, with contrast-enhanced MRI of the abdomen and pelvis should be substituted for full CT scanning if the CT frequency prescribed in [Table 8-1](#), [Table 8-2](#), and [Table 8-4](#) is not permitted per country or ethics requirements or if CT contrast is contraindicated. The method of imaging, including use of contrast, should be consistent throughout the study (i.e. if CT is done at screening, CT will be done at all future timepoints), where not contraindicated.
- A baseline MRI of the brain is required for all subjects. CT may be performed. Subsequent brain scans should only be performed as clinically indicated (e.g. symptoms suggestive of CNS recurrence). Contrast enhanced brain MRI is preferred, however, if MRI contrast is contraindicated, then MRI without contrast or CT with/without contrast is acceptable.
- Biopsy of suspected recurrences is strongly recommended to confirm the diagnosis.
- Ultrasound is not a suitable modality of disease assessment for distant metastases. If new lesions are identified by ultrasound, confirmation by CT or MRI is required.
- If clinically indicated, CT or MRI of other areas (e.g., neck) of disease as appropriate should be performed.
- Fluorodeoxyglucose positron emission tomography (FDG)-PET can be useful in confirming new sites of disease where a positive FDG-PET scans correlates with the new site of disease present on CT/MRI or when a baseline FDG-PET was previously negative for the site of the new lesion.
- If PET/CT is performed then the CT component can only be used for standard disease assessments if performed to diagnostic quality, which includes the required anatomical

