### 5.7.3 Handling of missing values/censoring/discontinuations

#### Censoring of RFS

If no event has occurred by the primary analysis cutoff, then RFS will be censored as the date of the last efficacy assessment (i.e. either radiological or non-radiological) prior to the analysis cutoff that shows no disease recurrence. Patient will be censored for RFS at the date of first treatment for any of the following situation:

- The censoring algorithm calls for the patient to be censored at the date of the last adequate assessment meeting a certain set of criteria (e.g. prior to subsequent anticancertherapy), but no such assessment exists.

RFS will be censored for extended loss to follow-up to account for missed efficacy assessments prior to relapse or death. Specifically, if there are two or more scheduled efficacy assessments which are missing during the first 12 months of the treatment period, two or more missing during the follow up period followed by an assessment of relapse or death (due to any cause), RFS will be censored at the last adequate assessment prior to relapse or death. If the time interval between the last adequate efficacy assessment date and the RFS event date is larger than the interval of 2 missing efficacy assessments (7 days for treatment phase and 14 days for follow-up phase, protocol-specified time window ) then the patient will be censored and the censoring reason will be 'Event documented after two or more missing tumor assessments. For this type of censoring, the 'last adequate assessment' is defined as the date of the last MRI or CT assessment prior to the missing assessments that shows no disease recurrence.

For patients who receive subsequent anti-cancer therapy the following rules will apply.

- If such therapy is started without evidence of documented disease recurrence, then RFS will be censored at the date of the last efficacy ) assessment before the date of initiation of anti-cancer therapy.
- If a patient has only a baseline visit or does not have an efficacy assessment before the date of initiation of anti-cancer therapy, RFS will be censored at the date of first treatment.

[Table 2-7](#) below further describes the algorithm to determine whether a patient should be classified as RFS event or censored.

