**Table 2-7 Outcome and event/censor dates for RFS analysis**

Situation	Date	Outcome
Recurrence documented between scheduled visits	Date of assessment of Recurrence	Event

Situation	Date	Outcome
No recurrence (or death)	Date of last efficacy assessment	Censored
New anti-cancer therapy (including surgery for melanoma) started prior to documented disease recurrence*	Date of last efficacy assessment on or prior to starting anti-cancer therapy	Censored
Death before recurrence assessment	Date of death	Event
Death between adequate assessment visits	Date of death	Event
Death or recurrence after two or more missed scheduled efficacy assessments during study treatment period or after two or more missing during the follow up period	Date of last adequate assessment prior to missed assessments	Censored

\*If relapse and new anti-cancer therapy occur on the same day then the relapse will be counted as event. If anticancer therapy is started prior to any adequate assessments, censoring date should be the date of first treatment.

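### 24-month RFS is likely to be biased downwards: relapse-free subjects leave the risk set on their own Month 24 scan date, and the curve is read after that visit window has closed

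*Protocol*

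**What the plan says.** **End of relapse assessment.** Protocol Section 3 states that "subjects will be followed from treatment discontinuation through 24 months from their first dose date for relapse". Section 4.1 adds that subjects remain in follow-up afterwards "but will only have on-study tumor assessments through 24 months after first dose of study treatment". The Protocol summary gives the schedule: "Tumor assessment by investigator's assessment measured at Month 3, 6, 12, 15, 18 and 24". For an end-of-study (EoS) visit after Month 24, footnote 3 of Table 8-2 says that "a clinic visit is not required and the information collected will be limited to the following", and goes on to name therapy, response and survival data. Table 8-4, however, lists an EoS scan for relapse-free subjects who have had none in the preceding 30 days.

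**Timing.** Protocol Section 3 sets one study month at 28 days. Section 8.3.1.1 gives the scan tolerance: "After Month 12/EoT a post-baseline assessment window of ± 14 days is permitted". SAP Section 5.1.1 (Time units) uses a month of 30.4375 days and a year of 365.25 days. SAP Section 5.7.2 reads the RFS curve at 1 and 2 years.

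**Event and censoring dates.** SAP Section 5.7.3: "If no event has occurred by the primary analysis cutoff, then RFS will be censored as the date of the last efficacy assessment". Protocol Section 12.5.1 likewise uses the last adequate tumor assessment. In SAP Table 2-7 (RFS outcomes) a recurrence is an event on its assessment date, and "Death before recurrence assessment" is an event on the date of death. No common visit date and no interval-censored estimator is specified for RFS.

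**The concern.** Kaplan-Meier assumes that a subject censored on a given day has the same future risk as those still under observation. Here the Month 24 scan itself decides the outcome. A clear scan removes the subject that day, and a scan showing relapse produces an event that day. Someone scanned early and found clear cannot serve in the denominator for someone scanned two weeks later and found relapsed, although both results describe the same visit. As the window runs out, the denominator goes to zero while relapses are still being recorded.

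24-month RFS is a named secondary endpoint, and Protocol Section 3 says that effectiveness will also be judged on RFS and OS. In a single-arm trial with a historical benchmark, an artificially low value could be read as a loss of efficacy under the adapted pyrexia algorithm.

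**Working it through.** **Inputs and days**

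- Month 24 visit: 24 × 28 + 1 = Day 673.
- Permitted scans: 673 ± 14 = Days 659 to 687, which is 29 days.
- Reading day: 24 × 30.4375 = 730.5, which is 730.5 − 687 = 43.5 days after the window closes.
- Benchmark (Protocol Section 12.7): 12-month RFS 88%, 95% CI 85-91%. N = 556 (SAP Section 4).

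The documents give no expected 24-month RFS, so there is no planned figure to reproduce. The benchmark is internally consistent: with n = 435, 0.88 ± 1.96 × √(0.88 × 0.12/435) = 84.9% to 91.1%.

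**By formula.** Let scans be spread evenly over the 29 days, and let a proportion p of those scanned be found relapsed. The correct factor for the visit is 1 − p. When j days of the window remain, the daily Kaplan-Meier hazard is p/j, so the curve is multiplied by the product of (1 − p/j) over j = 29, …, 1.

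| p | Correct factor | Kaplan-Meier factor |
|---|---|---|
| 3% | 0.970 | 0.887 |
| 6% | 0.940 | 0.786 |
| 9% | 0.910 | 0.695 |

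To link p to a 24-month rate, assume a constant hazard from 88% at Day 337 to S at Day 673, with every relapse found at a scheduled scan. The Month 18 scan (Day 505) lies halfway, so RFS there is 0.88 × √(S/0.88) and p = 1 − √(S/0.88). For S = 70%: RFS at Day 505 is 0.785, p = 0.108, and the factor is 0.645. The reported value is 0.785 × 0.645 = 50.6%. The same steps give 59.6%, 69.7% and 80.8% for true 75%, 80% and 85%.

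**By simulation.** N = 556, 88% at 12 months, scans uniform over their windows, SAP censoring, and 50-100% of relapses found at scheduled scans. The true rate is assumed and refers to the Month 24 visit.

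| True RFS | SAP rule, mean | Common censoring at Day 687 |
|---|---|---|
| 70% | 49-58% | 69.8-70.2% |
| 75% | 59-66% | 75.0-75.1% |
| 80% | 70-74% | 80.0-80.3% |
| 85% | 80-83% | 84.8-85.1% |

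The shortfall runs from 85 − 83 = 2 points to 70 − 49 = 21 points. Values at Days 687 and 730 were identical, so moving the reading day to the end of the window does not by itself cure it.

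**Sensitivity**

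- All scans exactly on Day 673: no bias (0.789 against a true 0.790 on that day; separate runs with constant hazard and 24-month RFS 0.88² = 0.774).
- Scan dates clustered around the target (SD 5 days): a larger mean loss. A true 70% reads 42-52% and a true 80% reads 63-70%, because a single late scan can meet a very small risk set.
- Curve read at Day 672: about 0 to 4 points too high.
- A later assessment in some subjects, true 80%: 76-78% if 20% have one, 78-79% if 50% do, 79-80% if all do.

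**Deaths soon after the scan.** A relapse-free death between the scan and Day 730.5 is an RFS event with almost nobody at risk. At assumed relapse-free death rates of 0.3% and 1% per year, with all scans on target, the mean fell from 0.786 to 0.693 and from 0.777 to 0.681. Some runs reached zero, which would also print a finite median. SAP Section 5.7.3 censors events that follow too long a gap since the last adequate assessment. For a death by Day 730.5 the gap is at most 730.5 − 659 = 71.5 days, less than even one of the shortest follow-up scan intervals (3 × 28 = 84 days), so a two-scan gap would not exclude it.

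**The case against.** The strongest reply is that relapse assessment may not end at Month 24. Table 8-4 asks for an EoS scan in relapse-free subjects, Table 8-2 marks CT at EoS, and its footnote waives a clinic visit without forbidding one. SAP Section 5.7.3 accepts non-radiological assessments too. EoS is 24 months after the last subject's Day 1, so for most subjects it comes well after their own Month 24. This stands in part: if many were assessed later, the bias would be small. But Section 4.1 and the footnote point the other way, and the plan should not depend on an unresolved conflict.

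Secondly, a reader might infer that the estimate is too low wherever it is read. The documents do not support that: at Day 672, which is 24 protocol months, the error is small and upward. The downward result follows from the SAP's own 30.4375-day month.

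Thirdly, a reader might infer that any death up to study end takes the curve to zero and spoils the 24-month figure. That is too strong. The elapsed-time rule in SAP Section 5.7.3 would censor deaths long after the last scan, and a death after Day 730.5 cannot change the 24-month estimate.

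Finally, RFS is analysed descriptively, without hypothesis or margin. It would be wrong to infer that the trial's conclusion rests on it. The primary pyrexia analysis is unaffected, and the interim looked at RFS at 6 months against a 12-month threshold.

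**Conclusion.** The point holds as a should-fix on a descriptive secondary endpoint. Under the rules as written, and if few subjects are scanned after Month 24, the Kaplan-Meier 24-month RFS is biased down. With assumed true rates of 70-85%, scans spread over the permitted window and at least half of relapses found at scheduled scans, the bias is about 2 to 21 points. None of those three assumptions comes from the documents. The bias shrinks with EoS scanning and disappears if all scans fall on one day. A relapse-free death soon after the Month 24 scan acts in the same direction and can create an artefactual median.

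**What to change.** In SAP Section 5.7.3 and Table 2-7, with matching text in Protocol Section 12.5.1:

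- Censor every subject found relapse-free at the Month 24 assessment at one common date, the end of the Month 24 window (Day 687). Subjects without a Month 24 assessment keep the present rule.
- Count relapses found at that visit on the scan date.
- Count deaths after the common date for OS only.
- Report 24-month RFS at Day 687, in the same 28-day months as the visits, with the number at risk.
- Reconcile the EoS scan line in Table 8-4 with Section 4.1 and footnote 3 of Table 8-2.

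The cost is a few lines of text and programming, plus a documented change to the protocol's censoring date. The downside is that a subject scanned on Day 659 is credited with up to 687 − 659 = 28 unobserved relapse-free days. An interval-censored estimate can serve as a sensitivity analysis.
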